5.4 Scheduled Procedures

The Principal Investigator is responsible for ensuring all clinical data is collected as required per CIP scheduled procedures. The data collection elements required for each study visit are summarized in Table 4 below.

Table 4: Summary of study procedures

Study activities and visits	Baseline	Index procedure	Pre-Dis	30 days	12-months**
Visit window	-180d-0	0	0-7d	30-120d	358-410d
Informed consent	X				
Demographics	X				
Medical and cardiovascular history	X				
Surgical risk assessment*	X				
Frailty assessment*	X				
Native aortic valve assessment*	X				
Access site assessment*	X				
Physical assessment	X		X	X	
Blood Work: § - Hemoglobin, Creatinine and Troponin	X		X	X	
NYHA class assessment	X			X	
Quality of Life questionnaire (EQ5D-3L)	X			X	
Implant characteristics		X			
Electrocardiogram (ECG) §	X			X	
Echocardiogram	X			X	
Anti-platelet and anti-coagulation medication assessment	X	X	X	X	
Assessment of resource utilization		X	X		
Adverse events assessment	X	X	X	X	
Vital status/mortality check					X

* Per standard of care testing for a TAVI and should be within 180 days prior to index procedure

**This visit may be completed via a phone call

§ If available

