5.4.2 Portico Valve Implant or Index Procedure

The medical team performing the TAVI procedure will typically consist of:

- An implanting physician (either an interventional cardiologist or a cardiac surgeon) at the center who will perform the procedure
- A second operator (a cardiac surgeon or a cardiologist) may be present during the procedure as needed

- An anesthesiologist and a perfusionist as needed for their own functions

NOTE: Anticoagulation use is left to the physician's discretion or should be established as with any other biological valve implantation, considering risks and benefits for the patient.

The implant procedure will be conducted per standard of care guidelines at each center, and in accordance with the product IFU and Sponsor's training program. The procedure will consist of the following activities:

1. Adverse events assessment
2. Document transcatheter aortic valve deployment information
3. Procedural characteristics
4. Procedural imaging (angiogram, intra-procedural echocardiography assessments) if available as part of standard of care
5. Resource utilization assessment

It is recommended to follow the peri-procedural instructions for the assessment of aortic regurgitation and implant depth as mentioned in Appendix E: Peri-procedural Guidelines. However, an implant center may follow their own standard of care practices and failure to follow these instructions will not be considered a protocol deviation.

During the procedure, the implanting physician may determine the implantation of the Portico valve is either not feasible or not in the best interest of the patient. Reasons for procedural exclusion may include, but are not limited to, anatomy that is not suitable for implantation, inability to gain access, ventricular arrhythmia, or any other contraindication.

If the implant procedure was not attempted (i.e. the Portico delivery system was never introduced into the subject's vasculature), the subject will not be considered enrolled. Refer to Section 5.3: Point of Enrollment.

If the implant procedure was attempted (i.e. the Portico delivery system was introduced into subject's vasculature) but the Portico valve could not be implanted (e.g. Portico attempted but other valve ultimately placed in the annulus), the subject will be withdrawn from the study after a 30-day adverse event collection period.

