5.4.3 Pre-discharge Visit

The pre-discharge visit will take place at the time of hospital discharge or within seven days after the index procedure, whichever occurs first. If the patient is expected to be discharged over the weekend, the discharge tests may be completed on the last weekday prior to discharge. The assessment will include:

- Physical assessment
- Blood sample (Creatinine, Hemoglobin, Troponin, if available, as part of standard of care)
- Anti-platelet and anti-coagulation medication assessment
- Adverse events assessment
- Pacemaker dependency assessment (as applicable)
- Data on resource utilization will be collected to determine the costs associated with hospitalization for a Portico implant procedure

5.4.4 30 Day Follow-up Visit

Each patient will return to the participating institution for a follow-up visit at 30 days (30+90 days) post index procedure. The scheduled visit window is calculated from the date of implant procedure.

The following procedures must be completed at the 30-day follow-up visit:

- Physical assessment
- Blood sample (Creatinine, Hemoglobin, troponin) if available as part of standard of care
- Echocardiogram*
- NYHA functional status classification
- Completion of QoL questionnaire (EQ5D-3L)
- Heart rate and rhythm assessment
- Anti-platelet and anti-coagulation medication assessment
- Adverse events assessment
- Pacemaker dependency assessment (as applicable)

Sponsor Representatives may be involved in providing support during the follow-up procedures.

* Each site will be responsible for performing and interpreting the 30-day follow-up echocardiogram using the VARC-2 definitions. Echocardiograms will be sent to an independent Echocardiographic Core Laboratory for further analysis. Exams should be recorded in DICOM format and should be de-identified prior to sending to the sponsor.

5.4.5 12 Months Vital Status/Survival Status

Each patient will have a survival status check at 12 months (-7 days, +45 days) post index procedure. The scheduled visit window is calculated from the date of implant procedure. The vital status check will be performed to determine patient survival at 12 months only and may be conducted via an in-office visit or by telephone call with the patient during the visit window.

Every effort should be made to contact the subject for the 12 month vital status/mortality check. The subject should not be considered 'lost to follow-up' until:

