5.10 Subject Study Completion

Subject participation in the clinical investigation will conclude upon completion of the 12 month vital status check. Upon completion of subject participation in the clinical investigation, the subject will return to standard of care.

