5.11 Subject Withdrawal

Each patient should remain in the investigation until completion of the required follow up period; however, a patient's participation in the investigation may be discontinued. Should this occur, the reason for discontinuation must be documented in the source documents.

Patients must be informed about their right to withdraw from the clinical investigation at any time and for any reason without sanction, penalty or loss of benefits to which the subject is otherwise entitled. Withdrawal from the clinical investigation will not jeopardize their future medical care or relationship with the investigator. Patients will be requested to specify the reason for the request to withdraw. The investigator must make all reasonable efforts to retain the subject in the clinical investigation until completion of the clinical investigation.

The investigator may decide to withdraw a patient from the investigation at any time. The patient's future care will not be influenced by a decision, voluntary or otherwise, to withdraw from the investigation. All reasonable efforts should be made to retain the patient in the clinical investigation until completion of the investigation.

For this registry, a patient will be considered 'lost to follow up' after

- A minimum of two phone calls from a physician or delegate at the implanting center have been attempted to reach the patient. These two phone calls must be documented in the patient's hospital records
- AND
- A letter has been sent to the patient's last known address or general practitioner (GP). A copy of this letter should be maintained in the patient's hospital records.

When subject withdrawal from the clinical investigation is due to an unsuccessful valve implant attempt, the subject will be followed for 30 days, until resolution of that adverse event, or determination that the subject's condition is stable. The status of the subject's condition should be documented at the time of withdrawal.

In case of subject withdrawal, the center should make attempts to schedule the subject for a final study visit.

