### 2.6 Timing of Analysis

Final analysis will be conducted after all enrolled subjects (First generation and Next generation Portico delivery system have either been terminated or completed the 12-month follow-up.

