### 3.3 Subject Early Termination

Reasons for early termination including deaths, withdrawals, lost to follow-up, unsuccessful implant, etc. will be summarized.

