## 5 ACRONYMS AND ABBREVIATIONS

Acronym or Abbreviation	Complete Phrase or Definition
AE	Adverse Event
AP	Attempted Procedure
CEC	Clinical Events Committee
CIP	Clinical Investigation Plan
CRF	Case Report Form
IP	Implanted Population
KM	Kaplan-Meier
NYHA	New York Heart Association
SAP	Statistical Analysis Plan
SD	Standard Deviation

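### Twelve-month mortality is estimated in all attempted implants, but subjects who receive no Portico valve are withdrawn at about day 30 and so censored because of their procedural outcome

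*Protocol*

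**What the plan says.** **Population.** Protocol 6.2 defines the analysis population by attempted implant, whether or not a Portico valve is left in place. SAP 2.3.6 runs all mortality analyses in the AP, which SAP section 5 expands as "Attempted Procedure", and uses Kaplan-Meier for the 12-month rate.

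**Follow-up after a failed attempt.** Protocol 5.4.2 states that when the delivery system was introduced but the Portico valve could not be implanted, "the subject will be withdrawn from the study after a 30-day adverse event collection period". Protocol 5.11 agrees in substance: "When subject withdrawal from the clinical investigation is due to an unsuccessful valve implant attempt, the subject will be followed for 30 days", with longer follow-up possible while an adverse event is unresolved. Protocol 5.3 guarantees only 30 days to every enrolled subject.

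**Status in the analysis.** SAP 3.3 treats the failed attempt as a reason to leave the study: "Reasons for early termination including deaths, withdrawals, lost to follow-up, unsuccessful implant, etc. will be summarized". SAP 2.6 runs the final analysis once all subjects "have either been terminated or completed the 12-month follow-up". SAP 2.2.3 censors at the last time a subject was known to be event-free, and SAP 2.8 imputes nothing.

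**Text that does not mention the exception.** Protocol 5.4.5 says "Each patient will have a survival status check at 12 months". Protocol 5.10 says "Subject participation in the clinical investigation will conclude upon completion of the 12 month vital status check". Table 4 in Protocol 5.4 shows the 12-month check for everyone and notes that "This visit may be completed via a phone call".

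**The concern.** Kaplan-Meier is unbiased only if censored subjects have the same later risk as those still followed. Here the censoring is neither administrative nor random. The protocol imposes it on everyone in whom the valve could not be implanted. Protocol 5.4.2 names unsuitable anatomy, failed access and ventricular arrhythmia as possible reasons for not implanting, so equal later risk is an assumption that the registry will have no data to test.

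All-cause mortality is the only endpoint carried to 12 months. Interim reports may be used for reimbursement (Protocol 6.7, SAP 2.5), and SAP 2.7 shows all endpoints side by side for the first-generation and FlexNav delivery systems. If the rate of failed implantation differs between the systems, the amount of outcome-dependent censoring differs between the two columns. What is at stake is a 12-month figure that does not describe the population it is stated for. No hypothesis test depends on it.

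**Working it through.** The plan states no 12-month mortality, failure rate or precision in visible text, so there is no planned figure to reproduce. The check is a two-period calculation.

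**Inputs**
- N = 1000 attempted implants, about 500 per delivery-system cohort (Protocol 6.5, SAP 1.3).
- f, share not implanted: 1%, 3%, 5% (assumed).
- d30s, day-30 mortality if implanted: 2.5% (assumed; Protocol section 2 reports 1.6% to 8.5% in other registries).
- d30f, day-30 mortality if not implanted: 2.5% to 15% (assumed).
- hs, mortality from day 30 to month 12 if implanted: 9% (assumed).
- hf, the same if not implanted: 1 − (1 − hs)^HR for a hazard ratio HR of 0.5, 1, 2 or 4, giving 4.61%, 9.00%, 17.19% and 31.43%; also hf = 40% as an extreme case.

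**Subjects censored.** The number is 1000 × f × (1 − d30f).
- Smallest: 1000 × 0.01 × 0.85 = 8.5.
- Largest: 1000 × 0.05 × 0.975 = 48.8.
- As a share of those alive at day 30: 8.5/973.75 = 0.87% to 48.75/975 = 5.00%.

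**Bias if all are censored at day 30**

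S_KM = [f(1 − d30f) + (1 − f)(1 − d30s)] × (1 − hs)

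S_true = f(1 − d30f)(1 − hf) + (1 − f)(1 − d30s)(1 − hs)

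S_KM − S_true = f(1 − d30f)(hf − hs)

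A positive value means that reported mortality is too low. Example with f = 5%, d30f = 2.5%, HR 2: 0.05 × 0.975 × (0.1719 − 0.09) = 0.40 points.

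| Later risk, not implanted | d30f = 15%; f = 1 / 3 / 5% | d30f = 2.5%; f = 1 / 3 / 5% |
|---|---|---|
| HR 0.5 | −0.04 / −0.11 / −0.19 | −0.04 / −0.13 / −0.21 |
| HR 1 | 0 | 0 |
| HR 2 | 0.07 / 0.21 / 0.35 | 0.08 / 0.24 / 0.40 |
| HR 4 | 0.19 / 0.57 / 0.95 | 0.22 / 0.66 / 1.09 |
| hf = 40%, f = 5% only | 1.32 | 1.51 |

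**Later censoring.** Protocol 5.11 can extend follow-up. As a late case, assume that all are censored at day 120, the end of the 30-day visit window in Table 4, with constant hazards λ over days 30–365:

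S_KM = [f(1 − d30f)e^(−90λf) + (1 − f)(1 − d30s)e^(−90λs)] × e^(−245λs)

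The overall range narrows from 0.21 too high / 1.51 too low to 0.16 too high / 1.04 too low.

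**Sampling error.** The 95% half-width is 1.96 × √(p(1 − p)/N).
- p = 11.28% (Kaplan-Meier mortality when d30f = 2.5%): 1.96 points at N = 1000 and 2.77 at N = 500.
- p = 13.16% (true mortality at f = 5%, d30f = 15%, hf = 40%): 2.10 and 2.96 points.

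**Bounds.** Setting hf to 0 and then to 1 gives none-die/all-die limits of width f(1 − d30f).

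| f | d30f = 15%: Kaplan-Meier, bounds | d30f = 2.5%: Kaplan-Meier, bounds |
|---|---|---|
| 1% | 11.39%, 11.31–12.16% | 11.28%, 11.19–12.16% |
| 3% | 11.62%, 11.39–13.94% | 11.28%, 11.01–13.94% |
| 5% | 11.84%, 11.46–15.71% | 11.28%, 10.84–15.71% |

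**Second calculation with other inputs.** With 3% day-30 mortality in both groups, 10% later mortality if implanted, 30% if not, and f = 3%, the formula gives 12.70% with day-30 censoring against 13.28% with full follow-up. A simulation of 400,000 subjects gave 12.68% and 13.24%.

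**The case against.** **Redaction.** SAP 2.1 is wholly blacked out and SAP 2.3.6 is blacked out on both sides of the Kaplan-Meier sentence. SAP section 5 lists an Implanted Population that appears nowhere else in the visible text. A censoring rule, a label or a supplementary analysis may sit there. This stands as a limit on the reporting half of the point, and the labelling request is conditional on it. It does not touch the follow-up half, because no analysis rule can supply vital status that was not collected.

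**The general 12-month check.** Protocol 5.4.5 and 5.10 make no exception, and Protocol 8.2 has deaths reported through one year. But 8.2 also ends safety reporting at withdrawal, and 5.4.2 and 5.11 are the specific rules for this group. The better reading is that they are an exception to the general check. On either reading the sections need aligning.

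**Purpose of the registry.** The objective concerns the Portico valve, so ending follow-up of subjects who received another valve or none is defensible. That would justify a 12-month estimate in implanted subjects. It does not justify one labelled for all attempts.

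**Size.** The bias is probably small, its direction is unknown, the endpoint is descriptive, and SAP 3.3 already discloses the overall count. All of this stands and limits the weight of the point. Sampling error, however, shrinks with N and can be read from N, whereas this bias does neither.

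**Uneven repair.** The cohorts enrol in sequence, so an amendment now could recover 12-month status mainly in the FlexNav cohort. That is a real drawback, largely met by reporting the count and the bounds for each cohort.

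**Conclusion.** The concern holds. Followed as written, the plan gives a 12-month mortality figure stated for all attempted implants whose course after about day 30 carries no information on those who did not receive the valve. On the assumed inputs, 9 to 49 of 1000 subjects would be affected and the error would run from 0.21 points too high to 1.51 points too low. It is zero if later mortality is the same in both groups, and 0.07–0.40 points too low at a hazard ratio of 2. All values lie below the sampling half-width of about 2.0–2.1 points at N=1000 and 2.8–3.0 at N=500. Thirty-day mortality is not affected, because these subjects are kept for 30 days. No conclusion would be reversed. This should be fixed because the figure does not match its stated population and the repair is cheap. The reading of the follow-up rule rests on visible text. The size rests entirely on assumed failure and mortality rates.

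**What to change.** 1. Amend Protocol 5.4.2 and 5.11 so that subjects with an attempted but unsuccessful implant end device-specific assessments at 30 days but keep the 12-month vital-status contact. Align Protocol 5.3, 5.4.5, 5.10 and Table 4. The death reporting in Protocol 8.2 would then cover these subjects without change, since they would no longer be withdrawn.
2. Where status cannot be obtained, for example in subjects already withdrawn, and unless the redacted SAP text already does so: state in the label of the 12-month estimate that these subjects were censored at about day 30, report their number by delivery-system cohort, and give none-die/all-die bounds overall and by cohort.

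**Cost.** One contact, which may be a telephone call, for an assumed 10–50 subjects, plus a protocol and consent amendment with ethics approval at up to 50 centers. No new visits or procedures are needed. The SAP cites guidance dated 28 April 2020, so some subjects may already have left; for them only the second step may be feasible, and it needs no new data.

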5.4.3 Pre-discharge Visit

The pre-discharge visit will take place at the time of hospital discharge or within seven days after the index procedure, whichever occurs first. If the patient is expected to be discharged over the weekend, the discharge tests may be completed on the last weekday prior to discharge. The assessment will include:

- Physical assessment
- Blood sample (Creatinine, Hemoglobin, Troponin, if available, as part of standard of care)
- Anti-platelet and anti-coagulation medication assessment
- Adverse events assessment
- Pacemaker dependency assessment (as applicable)
- Data on resource utilization will be collected to determine the costs associated with hospitalization for a Portico implant procedure

5.4.4 30 Day Follow-up Visit

Each patient will return to the participating institution for a follow-up visit at 30 days (30+90 days) post index procedure. The scheduled visit window is calculated from the date of implant procedure.

The following procedures must be completed at the 30-day follow-up visit:

- Physical assessment
- Blood sample (Creatinine, Hemoglobin, troponin) if available as part of standard of care
- Echocardiogram*
- NYHA functional status classification
- Completion of QoL questionnaire (EQ5D-3L)
- Heart rate and rhythm assessment
- Anti-platelet and anti-coagulation medication assessment
- Adverse events assessment
- Pacemaker dependency assessment (as applicable)

Sponsor Representatives may be involved in providing support during the follow-up procedures.

* Each site will be responsible for performing and interpreting the 30-day follow-up echocardiogram using the VARC-2 definitions. Echocardiograms will be sent to an independent Echocardiographic Core Laboratory for further analysis. Exams should be recorded in DICOM format and should be de-identified prior to sending to the sponsor.

5.4.5 12 Months Vital Status/Survival Status

Each patient will have a survival status check at 12 months (-7 days, +45 days) post index procedure. The scheduled visit window is calculated from the date of implant procedure. The vital status check will be performed to determine patient survival at 12 months only and may be conducted via an in-office visit or by telephone call with the patient during the visit window.

Every effort should be made to contact the subject for the 12 month vital status/mortality check. The subject should not be considered 'lost to follow-up' until:

- A minimum of two phone calls from a physician or delegate at the implanting center have been attempted to reach the patient. These two phone calls must be documented in the patient's hospital records

AND

- A letter has been sent to the patient's last known address or general practitioner (GP). A copy of this letter should be maintained in the patient's hospital records.

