8.2 Safety Reporting

Safety surveillance within this study and the safety reporting performed both by the Investigator (per local country requirements) and Sponsor commences at the time of procedure.

The safety surveillance and the safety reporting will continue until the final study visit has been performed, the subject is deceased, the subject/Investigator concludes their participation into the clinical investigation or the subject withdraws from the clinical investigation.

All adverse event data will be collected through the 30 day visit and will be reported to the Sponsor through the electronic data capture system (EDC). All deaths will be collected throughout the clinical study and will be reported to the Sponsor through the EDC using the applicable CRF. The Investigator will record all reportable adverse events and deaths on the appropriate case report forms.

Records relating to the subject's subsequent medical course must be maintained and submitted (as applicable) to the Sponsor until the event has subsided or, in case of permanent impairment, until the event stabilizes and the overall clinical outcome has been ascertained. Adverse events will be monitored until they are adequately resolved, the subject is withdrawn, or completes the study. At the 1 year vital status check, only mortality status will be collected.

For the purposes of this clinical investigation, the following events will be reported through the 30 day follow up visit with deaths reported through one year. All adverse events will be reported as soon as possible. Serious Adverse Events will be reported no later than 3 calendar days after becoming aware of the event or as per the investigative site's local requirements, if the requirement is more stringent than those outlined (see Appendix B: Definitions).

1. VARC-2 Adverse Events
 - Death

- Myocardial infarction
 - Vascular access site and access-related complications
 - Stroke/TIA
 - Bleeding events
 - Acute kidney injury
 - Coronary Obstruction
 - Pacemaker
2. All Adverse Device Effects
 3. All Serious Adverse Events (whether or not the event is considered device or procedure related)

Non-serious adverse events documentation and reporting are limited to cardiovascular and neurovascular events only; all events must be reported regardless of their relationship with the device or the procedure.

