##### 2.2.3 Survival Analysis

Survival analysis will be conducted to analyze time-to-event variables. Subjects without events will be censored at their last known event-free time point. Survival curves will be constructed using Kaplan-Meier (KM) estimates.

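### The minimum lost-to-follow-up rule lets a site stop before asking anyone but the patient, so some deaths may be censored and 12-month mortality may be underestimated

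*Protocol*

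**What the plan says.** All-cause mortality at 12 months is part of descriptive endpoint 6 (Protocol 4.3 and 6.3; SAP 1.4), and mortality status is the only item collected at that time (Protocol 8.2).

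- **Route.** Protocol 5.4.5 says the check "may be conducted via an in-office visit or by telephone call with the patient during the visit window". The window in Table 4 is day 358 to 410.
- **Effort.** The same section states: "Every effort should be made to contact the subject for the 12 month vital status/mortality check".
- **Lost to follow-up.** Two conditions must both be met. The first is "A minimum of two phone calls from a physician or delegate at the implanting center have been attempted to reach the patient". The second is one letter, addressed to the patient's "last known address or general practitioner (GP"). Neither condition requires an answer. Protocol 5.11 repeats the rule, introduced by "For this registry, a patient will be considered 'lost to follow up' after", without the effort clause.
- **Deaths.** Protocol 8.2 states: "All deaths will be collected throughout the clinical study and will be reported to the Sponsor through the EDC using the applicable CRF". Under 8.2.1 a death is reported within 3 calendar days of the site becoming aware of it.
- **Contact between visits.** Table 4 has nothing between the 30-day visit (day 30-120) and the 12-month check. Protocol 5.6 defines unscheduled visits only up to the 30-day visit.
- **Analysis.** SAP 2.2.3 states: "Subjects without events will be censored at their last known event-free time point". SAP 2.3.6 uses Kaplan-Meier for 12-month mortality, and SAP 2.8 imputes nothing. SAP 3.3 summarises reasons for early termination, including loss to follow-up. The only sensitivity analysis visible in 2.3.6 concerns COVID-19; parts of that section are redacted.

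**The concern.** The check exists to learn whether the patient is alive, yet its named routes depend on the patient responding. Suppose a patient dies at home in month 6, nobody answers two calls, and a letter goes to the same address. The site has then met the minimum rule without asking the GP, a relative, the hospital record system or a register. If nobody volunteers the news, the subject is recorded as lost and censored, most likely at the 30-day visit, because no later contact is scheduled.

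If dead patients are harder to reach than living ones, censoring depends on the outcome. Kaplan-Meier assumes that it does not, and would then give too low a mortality. What is at stake is the one long-term outcome of the registry, which SAP 2.7 also presents side by side for the two delivery-system cohorts.

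**Working it through.** The documents give no expected loss rate and no 12-month mortality figure, and the sample-size rationale is redacted, so there is no stated figure to reproduce. Only the window can be checked: 365 - 7 = 358 and 365 + 45 = 410, as in Table 4. Everything below is an illustration on assumed rates.

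**Method.** Treat lost subjects as censored just after the 30-day visit. Let d be mortality to that visit and q the observed proportion dying afterwards among those followed. Then KM(12 months) = 1 - (1 - d)(1 - q).

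**Deaths missed, no survivors lost.** Assume n = 1000, d = 3% and true 12-month mortality 12%. That is 30 early deaths, 970 survivors and 90 later deaths. The truth is 1 - 0.97 × 880/970 = 12.0%.

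| Later deaths missed | Subjects lost | Observed q | KM estimate | Shortfall |
|---|---|---|---|---|
| 10% | 9 | 81/961 = 8.43% | 11.2% | 0.8 points |
| 20% | 18 | 72/952 = 7.56% | 10.3% | 1.7 points |
| 30% | 27 | 63/943 = 6.68% | 9.5% | 2.5 points |

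These losses are 0.9% to 2.8% of 970, so a low overall loss rate would not by itself rule the problem out.

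**Sampling error for scale.** 1.96 × sqrt(0.12 × 0.88/1000) = 2.0 points. With 500 per cohort it is 2.9 points (2.85). Only the 30% row exceeds the first, and no row reaches the second.

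**Changing who is lost, same assumptions.**

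- 20% of later deaths missed and 5% of survivors lost (44): 970 - 18 - 44 = 908 followed. 1 - 0.97 × (1 - 72/908) = 10.7%, which is 1.3 points low.
- 10% of deaths and 10% of survivors lost: 81/(81 + 792) = 9.28%, the same as 90/970. KM is 12.0%, with no bias.
- No deaths missed and 5% of survivors lost: 1 - 0.97 × (1 - 90/926) = 12.4%, which is 0.4 points high.

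**A wider grid.** Take d = 2.2% (quoted for one newer valve in Protocol section 2), true 12-month mortality of 10%, 12% or 15%, and a share L of 30-day survivors lost of 2%, 5% or 10%. If the lost die at r times the rate of those followed, q = q_true/[(1 - L) + rL].

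- r = 1: bias is zero.
- r = 1.5 to 3: KM is 0.08 to 2.13 points too low. For example, at 12% true mortality, L = 5% and r = 2: q_true = 1 - 0.88/0.978 = 10.0%, q = 10.02%/1.05 = 9.54%, and KM = 11.5%.
- All deaths known and only survivors lost, so q = q_true/(1 - L): KM is 0.16 to 1.42 points too high.

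**Bounds.** For an observed KM of 12% with d = 2.2% and 5% of 30-day survivors lost: all lost alive gives 1 - (0.95 × 0.88 + 0.05 × 0.978) = 11.5%; all lost dead gives 1 - 0.95 × 0.88 = 16.4%.

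**The case against.** The strongest reply is that the two calls and the letter are a floor, not the procedure. The effort clause stands directly above the rule in 5.4.5, and the GP is a named addressee. The wording on routes is permissive, and Protocol 4.1 and the Table 4 footnote allow a phone call without saying with whom. A relative who answers can report a death, and sections 8.2 and 8.2.1 would then require it to be recorded with source documents. Centralised monitoring (Protocol section 10) looks for missing data. The registry is descriptive, with no hypothesis tests.

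Much of this stands. A month-6 death is missed only if the calls go unanswered, the letter brings no response and the site does not hear of it some other way. Censoring at the 30-day visit is an inference: the SAP rule uses the last time the subject was known to be event-free, and undocumented-in-schedule contacts could extend it.

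It does not close the gap. The effort clause is about contacting the subject and names no other source. The reporting duty begins once the site knows of a death and does not make the site look for one. The GP remains optional.

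A reader might infer that 12-month mortality will be biased low, or that unequal searching, for example during the pandemic, will show up as a survival difference between cohorts. The documents support neither. They give no loss rate, no mortality among the lost and no sign that search effort differs by cohort, and SAP 2.2.4 announces efforts to limit missing endpoint data during the pandemic. The redacted text in SAP 2.3.6 may contain further 12-month handling, although no analysis recovers a death that was never ascertained.

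**Conclusion.** The concern holds in conditional form. The stated minimum rule can be met without any indirect check of vital status, so some deaths may go undetected and be censored, and Kaplan-Meier 12-month mortality may be underestimated. Downward bias is the main risk because the named routes rely on the patient responding; zero or upward bias is also possible.

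On the assumed figures of 3% and 12% with 1000 subjects and no survivors lost, the shortfall is 0.8 to 2.5 points when 10% to 30% of later deaths are missed. It exceeds the overall sampling half-width only in the 30% case and stays below the per-cohort half-width throughout. The proportions missed are assumptions with no support in the documents. This does not undermine the registry, but it is worth correcting because the remedy is cheap and protects the estimate whichever way the bias runs.

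**What to change.** **Protocol 5.4.5 and 5.11.** Require the letter to go to both the last known address and the GP. Before a subject is declared lost, require a documented attempt at indirect ascertainment: GP, next of kin, hospital records and, where national law and consent permit, the death register. Accept vital status from these sources as completing the 12-month check, and record its source and date on the eCRF.

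**SAP 2.3.6 and 2.7.** Report the percentage with known 12-month vital status by delivery-system cohort. Beside the Kaplan-Meier estimate give two bounds, one counting all lost subjects as alive and one counting all as dead; the worst case alone would be one-sided. Subjects withdrawn by rule after a failed implant are a different group and should be counted separately from those lost.

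**Cost.** Wording changes, one eCRF field for source and date, and a few extra contacts for subjects who cannot be reached. The downside is minor site work and, in some countries, an added consent line.
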